12.4 Inclusion of Women and Minorities (Special Populations)

Inclusion of Women

The proposed research is focused exclusively on women in the prenatal and postpartum period. The sample selected will be representative of this and other urban obstetric services. Men will not be included as primary study participants, given the focus on prevention of drug use in pregnancy. (However, note that approximately have of the 10 medical staff included as focus group members will be men.)

Inclusion of Minorities

Based on the demographics of Detroit, and of previous samples recruited in a similar manner from Wayne State University/Detroit Medical Center clinics, it is expected that the sample recruited in the proposed research will be primarily composed of racial and ethnic minorities. Specifically, we expect approximately 85% of participants to be African-Americans, 10% of participants to describe themselves as "Other" or to select

multiple racial categories, and 5% of participants to be White; approximately 10% will be of Hispanic ethnicity.

This sample, while not generalizable to the entire U.S. population, will be quite similar to other samples found in urban health care settings. Such a population, in and of itself, is worthy of study given (a) the increased rate of marijuana exposure among children of African-American mothers; (b) the clear disparities in the likelihood with which African-Americans and other minorities receive services related to substance abuse; and (c) the confluence of risks to children being delivered in urban hospitals serving low-income populations. If the data gathered for this clinical trial justify future research, that research will seek to validate technology-based screening and computerized intervention with tailored text messages in other samples of women using marijuana during pregnancy.

12.5 Subject Confidentiality

Subject confidentiality is strictly held in trust by the investigators, study staff, and the sponsor(s) and their agents. This confidentiality is extended to cover testing of biological samples and any study information relating to subjects.

The study protocol, documentation, data, and all other information generated will be held in strict confidence. No information concerning the study or the data will be released to any unauthorized third party without prior written approval of the sponsor. The authorized representatives of the sponsor may inspect all study documents and records required to be maintained by the investigator, including but not limited to, medical records (office, clinic, or hospital) for the study subjects. The clinical study site will permit access to such records.

Breaches of confidentiality will be prevented in a number of ways. First, we will strictly separate identifying information and data, connecting them only via a linking table (with a hard copy kept in a locked file cabinet in the PI's lab, and a password-protected electronic version kept on a secure WSU server). Old versions of the paper linking table will be shredded; the table will only be accessible by the PI and Project Coordinator. Second, breaches will also be prevented by encrypting all ACASI data in transit using AES-256 encryption (the highest level possible). Third, breaches will be prevented by further protecting saved data with extremely strong passphrases (combining capital letters, lowercase letters, and numbers, using at least 12 characters, and changing them monthly). Fourth, all study computers will be protected with a very strong passphrase.

Should a breach be discovered, it will be reported within 24 hours to the WSU IRB and to NIDA officials, followed by a written report within 72 hours. In addition to addressing

and correcting the source of the breach, discussions with the IRB, the study DSMB, and NIDA will determine whether study participants must be notified of the breach.

Certificate of Confidentiality

To further protect the privacy of study subjects, a Certificate of Confidentiality has been obtained from the NIH. This certificate protects identifiable research information from forced disclosure. It allows the investigator and others who have access to research records to refuse to disclose identifying information on research participation in any civil, civil, criminal, administrative, legislative, or other proceeding, whether at the federal, state, or local level. By protecting researchers and institutions from being compelled to disclose information that would identify research subjects, Certificates of Confidentiality help achieve the research objectives and promote participation in studies by helping assure confidentiality and privacy to subjects.

13 DATA HANDLING AND RECORD KEEPING

13.1 Data Management Responsibilities

Data collection and accurate documentation are the responsibility of the study staff under the supervision of the investigator. All source documents and laboratory reports must be reviewed by the study team and data entry staff, who will ensure that they are accurate and complete. Unanticipated problems and adverse events must be reviewed by the investigator or designee.

13.2 Data Capture Methods

Most data will be collected using computer-based self-interview (ACASI) technology on a Tablet computer, with data being encrypted in transit and stored on a secure server; further, all data in the ACASI system will only be identified only with a non-identifying ID number for the participant. A single paper copy of the table linking this number to the participant's name will be kept locked in a file cabinet in the PI's lab, with a password protected electronic version stored on a secure WSU server with restricted access, such that only the PI and the Project Coordinator will have access to the server and to the passwords for the linking table file. The PI's lab is kept locked, in a locked and alarmed secure building on campus.

Three additional sources of data will not be collected directly from the participant using the ACASI system. First, data will also be obtained from hair and urine testing performed at follow-up. These samples will also be identified only using the non-identifying participant ID number; the commercial labs doing testing the samples will never obtain identifying information on any participant. Further, data from this testing will not be available until after the participant has been discharged from the hospital, further limiting the potential for any negative consequences relating to prenatal drug exposure. Second, data will be obtained by DMC clinic staff from the neonate's electronic medical record (EMR). We will provide this staff person—who will already have access to clinic medical records—with the participant's name and date of birth, the infant's name and date of birth, and other information as needed so that she can accurately identify the infant in question. She will record birth weight, length of stay, and number of days in neonatal intensive care (if any) on a paper form containing only the participant ID number.

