1.3 Potential Risks and Benefits

1.3.1 Potential Risks

The primary potential risk of this type of research involves legal/child protective services repercussions due to drug (marijuana) use during pregnancy. Some additional risk may be present due to potential distress regarding evaluation of multiple sensitive areas.

We believe that the risks to participants in this study are minimal, particularly given the positive nature of the intervention and the plan to seek a Federal Certificate of Confidentiality. We believe that the minor risks that are present are justified given the tremendous potential of this research to produce: (a) a method of identifying a large proportion of women using marijuana during pregnancy; and (b) two replicable, high-reach, and low-cost interventions that are designed for pregnant women. These interventions, then, could potentially be presented to large numbers of pregnant women in a way that is financially and logistically feasible

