5.1 Screening

Participants will be 80 pregnant women at less than 20 weeks gestation, recruited from a WSU UPG Ob-Gyn clinic or Thea Bowman. Participants will be excluded if they are considering termination of the pregnancy or giving the baby up for adoption, are planning to deliver outside of the DMC Hutzel Hospital (over 90% of patients at this clinic deliver at Hutzel), are deemed unable to understand the consent process, or are unable to understand spoken English. Note that participation in this phase will be anonymous, and will use an informed consent information sheet rather than written consent, since collecting identifying information would present unnecessary risk (45 CFR 46.117). We have had clear success using a similar approach in prior studies. Past samples have been predominantly African-American and low-income (e.g., Ondersma, et al., 2007).

Screening and recruitment

Participants will be given a flyer by clinical staff at the clinics, alerting them to the existence of a voluntary study. Medical staff will indicate that the flyer describes a voluntary research project that involves 5-10 minutes to determine eligibility for a larger study and that they will receive a small gift for their baby if they choose to participate. Those showing tentative interest will be introduced to the research assistant, who will pre-screen for age, weeks gestation, ability to understand spoken English, and ability to receive and comfort receiving text messaging. Women passing this pre-screen process will be brought to a private room within the clinic where pre-screening will continue (i.e., intention to carry pregnancy to term). Those meeting this final pre-screen criterion will then be helped to review an informed consent information sheet (as used in prior NIH funded and IRB-approved studies; see 45 CFR 46.117). Those providing consent will use a Tablet PC with headphones (with disposable sanitary covers) to complete a brief screener evaluating a range of pregnancy-related health behaviors and emotions (e.g., nutrition, sleep, exercise, depression, anxiety, alcohol use, and smoking), as well as a key question regarding any marijuana use in the month prior to pregnancy. (See recruitment script in section 3.2)

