Hi, Congratulations on your pregnancy! My name is ______; I'm from Wayne State University. We are looking for pregnant woman to help with a research study. It will take 5-10 minutes to complete. First off the study is completely voluntary. Whether or not you participate will not affect your care at the clinic in any way. Also, no information that you give us will be shared with any of the staff. It's completely anonymous, which means your name is not recorded anywhere. You also get a gift for your baby for participating. All family members must wait in the waiting room until we're done, and we ask this of everyone that participates. Does this sound like something you'd be interested in? If the potential participant agrees, the RA may continue with screening:

Great! The first step is to just ask a couple questions to make sure you are eligible (ask age, due date, acceptance of texting, etc.). Now I can get you set up on the tablet. Normally we would go through an information sheet together; however, the tablet will read the information sheet to you. As you go along, if you have any questions or concerns please stop and ask me. The tablet will then ask you a range of questions related to your health and any substances you may or may not use.

This portion will help determine whether you are eligible for a study; if you are eligible, I'll tell you all about it when you are done. You can decide then if you're interested. I will stay in here just in case you have any questions.

- 2. Begin the Qualtrics screener. Give the participant the tablet and headphones. Show them where the volume controls are.
- 3. After the participant is done, Qualtrics provides a message saying "You are all done with this screener. Thank you very much for answering these questions! Please just give this computer to the research assistant. RA please press continue." When you press continue you will either see Ineligible or a color. If there is a color, they are eligible. Press continue again to receive their Qualtrics ID (it will be a 14 digit alphaneumeric id). Write both the color and ID number on the checklist; they will need to be entered into CIAS.
- 4. If participant is not eligible, RA thanks the participant, gives her a small baby gift, information sheet, and moves on.
- 5. If the participant is eligible and is interested in the RCT, the RA will give the participant the informed consent for Clinical Trial.

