2.	If you decide not to take part in this study, will the care you receive at UPG, Thea Bowman, or the DMC be affected?	NO
3.	How many visits will you be asked to participate in for this study?	2
4.	When will the second visit occur?	_ after delivery

If participant does not provide correct answer, record the answer and review the consent form. Repeat quiz; Questions 1 and 2 must be answered correctly on first or second attempt to continue in the study.

Have participant complete (and RA review):

- a) Future Research Contact form
 - [name] often has new studies that you might be interested in; we want to know if we can contact you about studies in the future. We would only contact you to tell you about a new study. If you're interested you will go through a consent process just like this. On a separate page is a box for you to check telling us whether or not we have your permission to contact you about future studies.
- b) Contact Form

Once all forms are complete and her questions are answered say:

- OK let's get started. The next part is to use the program on the tablet. It will walk you through it just like before and let you know what group you have been put in. Here are the headphones. If you get stuck, or have any questions, just ask me. Ready...
- 6. Open the tablet to the .mobi site and put in participants first name (spelled correctly), the Qualtrics ID (under MISC), and your initials (under staff initials). Here you will need to enter the participant's phone number in case they are placed in a text message group. Please let the participant know that the computer will place them into the group and tell them which group they are in. Since we do not know yet their group, you need to put in everyone's phone number. They will only get messages if they are in a texting group.

Ask them what days of the week and times during the day are okay to receive text messages. The texts will only come during the selected days and times. Ask them the frequency they said on the screener and select from the drop down menu from opt-in days (once/week, twice/week, three times/week).

Also, make sure you select US/Eastern time zone at the bottom.

Press login, write down the CIAD ID and start the program. You will need to re-enter the Qualtrics ID number in the text box and select the color. Then you can hand the tablet & headphones to the participant. (Hit next, select full screen).

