For the pilot randomized trial, we will utilize written informed consent for those who meet all inclusion and exclusion criteria. This consent form will be summarized by the research assistant and also read, if the participant wishes; a brief verbal quiz will check for understanding, and those failing the quiz twice will not be included in the study. The consent form will describe the nature of the two possible interventions, the kinds of questions that will be asked, the request for consent to allow limited access to their and their child's electronic medical records, follow-up procedures taking place post-partum (including being asked to give urine and hair samples to be tested for marijuana as well as cotinine, cocaine, amphetamines, barbiturates, and opiates), the participant's right to decline or guit at any time, and the possibility of distress as a result of some of the questions or material. Participants will also be told that their data will be identified by a code number only, with the only link between that code and their data being a single form kept locked in the PI's office. We have obtained a Federal Certificate of Confidentiality in order to protect participants against forced disclosure of their data; participants will be told of this additional protection, presuming our application is successful. Finally, although we will not ask any questions that might elicit reportable information in these areas, the consent form will clearly note the possible need to breach confidentiality should the investigators become aware of reportable information regarding child abuse, neglect, suicide risk, or infectious disease.

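### Enrolment steps enter first name, phone number and screener ID in CIAS for all 80 enrolled women, contradicting the statements that ACASI data carry only a non-identifying ID

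*Combined protocol and SAP*

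**What the plan says.** The main risk is named in Section 1.3.1: "The primary potential risk of this type of research involves legal/child protective services repercussions due to drug (marijuana) use during pregnancy". Four statements describe how data are kept apart from identity.

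- Section 13.2 (Data Capture Methods): "all data in the ACASI system will only be identified only with a non-identifying ID number for the participant".
- Section 12.5 (Subject Confidentiality): "we will strictly separate identifying information and data, connecting them only via a linking table". Access to that table is limited to the PI and the Project Coordinator.
- Section 12.3 (Informed Consent Process) gives the assurance made to trial participants: "their data will be identified by a code number only, with the only link between that code and their data being a single form". Staff hold this document under lock.
- Section 5.1 (Screening): "Note that participation in this phase will be anonymous". The recruitment script tells the woman: "It's completely anonymous, which means your name is not recorded anywhere".

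Section 5.2 gives the steps after trial consent. Step 6 has the research assistant open the program and "put in participants first name (spelled correctly), the Qualtrics ID (under MISC), and your initials". The phone number goes in at the same point for every arm: "Since we do not know yet their group, you need to put in everyone's phone number". The Qualtrics ID is then typed a second time inside the program. The clinical trial checklist in the same section repeats the Qualtrics ID entry and has lines for the Qualtrics ID, the cell number and the CIAS ID on one form.

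**The concern.** Step 6 places a direct identifier (the phone number) and a weak one (the first name) at the CIAS login that opens the woman's assessment session, together with the key to her screener record. That is a second route from identity to data, outside the restricted linking table.

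Three things are at stake. First, what women are told in the consent process about a single link would be inaccurate. Second, the screener record, given under a promise of anonymity, becomes traceable for those who enrol. Third, the IRB and the DSMB, which advises on confidentiality, would be judging a data flow that differs from the one staff are instructed to follow. No endpoint, estimate or error rate is affected directly. The point concerns participant protection and the accuracy of the protocol.

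**Working it through.** The plan gives no figure to reproduce. The check is a comparison of sections and one count.

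**1. Is CIAS the ACASI system?** Yes. Section 3 (Measures) says the study measures are given through the ACASI function of CIAS. Section 13.2's statement about ACASI data therefore applies to CIAS.

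**2. What does CIAS receive at enrolment?** Section 5.2, step 6: first name, Qualtrics ID and phone number, before allocation, for every woman who has signed the trial consent.

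**3. Are these fields used only to log in?** Not for texted women. Section 4.1 places the texting software within CIAS and says that messages use the first name.

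**4. Does the chain continue?** The Section 5.3 follow-up checklist has the baseline CIAS ID entered in the follow-up CIAS record, and the urine and hair samples are labelled with the follow-up CIAS number. So the sample code leads to the follow-up record, that leads to the baseline CIAS ID, and that ID belongs to a login at which a phone number was entered.

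**5. Side by side**

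| Statement | Enrolment procedure |
|---|---|
| ACASI data carry a non-identifying ID only (13.2) | First name and phone number entered in CIAS (5.2, step 6) |
| Identity and data joined only by the linking table (12.5, 12.3) | Name, phone number and screener ID entered at one CIAS login; cell number and both IDs on one checklist (5.2) |
| Screening is anonymous (5.1) | Screener ID entered beside name and phone number once she enrols (5.2) |

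No section says that CIAS stores contact fields apart from responses, deletes them for women who are not texted, or removes the Qualtrics ID.

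**6. Count.** Allocation from Section 3.3.1: 20 Control, 20 eSBIRT, 20 Text, 20 Both.

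- Entered in CIAS: 20 + 20 + 20 + 20 = 80 of 80.
- Number needed in CIAS for texting: Text 20 + Both 20 = 40 of 80.
- Number not needed there for texting: Control 20 + eSBIRT 20 = 40 of 80.

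**7. Who is outside the count.** Women who screen ineligible or decline the trial never reach step 6, so their screener records stay anonymous under the text.

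**The case against.** The strongest reply is that the conflict is one of wording in a single layer and that much of the protection is untouched. Most of this stands.

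- A reader might infer that the protection against the named risk is absent. The documents do not support that. The Certificate of Confidentiality (Section 12.5) covers identifiable data against forced disclosure whatever CIAS holds, and encryption and strong passphrases remain.
- A reader might infer that one breach of CIAS would expose identified drug-use answers. That is not shown. CIAS's internal storage is not described, and contact fields may sit in a separate table. Screener answers are collected in Qualtrics, so reaching them would also need access there. The 10 screen-only women have no baseline battery.
- A reader might infer that the waiver of signed consent for screening (Section 12.3) fails. It covers a stage at which no name is recorded; step 6 comes after written consent.
- A reader might infer that the breach-reporting rule in Section 12.5 depends on data being coded. It sets reporting times and a discussion about notifying participants, and works either way.
- A reader might infer that 40 phone numbers serve no purpose. Reminder calls are made in all arms (Sections 3.2 and 5). What those calls do not require is a number in CIAS, because Section 5.2 has a separate Contact Form.

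The consent form is not in the reviewed text, so it may already disclose the link. Section 12.3's summary of what participants are told points the other way.

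None of this removes the contradiction between step 6 and Sections 12.3, 12.5 and 13.2.

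**Conclusion.** The concern holds as a contradiction between a written procedure and a written safeguard. For all 80 planned participants, Section 5.2 has first name, phone number and screener ID entered in the system that Section 13.2 says carries only a non-identifying ID. For 40 of the 80, texting gives no reason to hold the number there. Enrolled women's screener records become linkable after consent; other screened women are unaffected.

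The conclusion is limited to one layer of protection being misdescribed. It does not show that a breach occurred or that identified answers could be read from CIAS alone. It assumes that allocation follows the planned 20 per group and that the Contact Form, whose content is not shown, carries the phone number used for reminder calls. The correction should be made because the layer concerned guards against the main risk the protocol names and the remedy is cheap.

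**What to change.** 1. **Reconcile** Section 5.2 (step 6 and the checklist) with Sections 12.3, 12.5 and 13.2, stating what CIAS holds, where, and who can see it.
2. **Separate the fields.** Keep name and phone number apart from response data and out of the response dataset.
3. **Limit phone numbers in CIAS to the text arms.** Where CIAS allows, enter the number only after the step 7 screen shows that the woman will receive texts. The documents do not show whether CIAS can accept a number after allocation; if it cannot, delete the number for the other arms once allocation is known. Take reminder-call numbers from the Contact Form.
4. **Keep the screener link but disclose it.** The screener is the only marijuana information before allocation that the documents show for screen-only controls, and the Section 9.3 models adjust for baseline frequency. State in Section 12.3 and the trial consent that the screener record will be linked on enrolment.
5. **Qualify the Section 5.1 script** so that it says answers stay anonymous unless the woman joins the trial.

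The cost is a small workflow change and an IRB amendment to the protocol, script and consent. The downside is a slightly less absolute promise at screening. Section 5.1 relies on anonymity to reduce under-reporting, so a little disclosure might be lost; the documents give no basis for sizing that loss.
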